### 3) Nitrotyrosine

The ELISA kit to measure Nitrotyrosine will be purchased from Cayman chemical (Cayman, Ann Arbor, MI). The kit consists of a 96 well plate, buffers and standard solution. The protocol to measure Nitrotyrosine in human serum or plasma will be strictly followed as provided with this commercial kit. All reagents needed for the assay are provided by the company and will be stored and used according to their recommendations. Particular quality control measures will include the following: When not in use, kit components will be refrigerated. All reagents will be warmed to room temperature before use. Microtiter plates will be allowed to come to room temperature before opening the foil bag. Once the desired number of strips has been removed, the bag will be resealed immediately and stored at 2 – 8°C to maintain plate integrity. Samples will be collected in pyrogen/endotoxin free tubes. Samples will be frozen shortly after collection (1-2 hours) in 500 µl aliquots and stored at – 20°C to –80°C until further processing, and send on dry ice to the laboratory at CHORI where they will be stored at –80°C, until analysis. Multiple freeze-thaw cycles of frozen samples will be avoided. The sample will be thawed completely and mixed well prior to analysis. When possible, badly hemolyzed or lipemic serum will be avoided. When large amounts of particulate matter are present, samples will be centrifuged or filtered prior to freezing, and a note will be added to indicate this treatment. All Standards, controls and samples will be run in duplicate. When pipetting reagents, a consistent order of addition will be maintained from well to well. This ensures equal incubation times for all wells. All reagents will be capped when not in use. Reagents from lots from various kit lots will not be interchanged or mixed. Reagents will not be used after the kit expiration date. Within 2 hours of assay completion, absorbance will be read. In-house controls will be run with every assay. If control values fall outside pre~stablished ranges, the accuracy of the assay is suspect, and will be repeated. All residual wash liquid will be drained from the wells by efficient aspiration or by decantation followed by tapping the plate forcefully on absorbent paper. Never will absorbent paper be inserted directly into the well. Because stabilized Chromogen is light sensitive, prolonged exposure to light will be avoided.

#### 4) 8-iso-PGF2 $\alpha$

The ELISA kit to measure 8-iso-PGF2 $\alpha$  will be purchased from Cayman chemical (Cayman, Ann Arbor, MI). The kit consists of a 96 well plate, buffers and standard solution. The protocol to measure 8-iso-PGF2 $\alpha$  in human serum or plasma will be strictly followed as provided with this commercial kit. All reagents needed for the assay are provided by the company and will be stored and used according to their recommendations. As serum or plasma may contain compounds that interfere with the assay, the samples will be purified according a standard protocol, using 8-isoprostane affinity column solid phase extraction purchased from Cayman chemical (Cayman, Ann Arbor, MI). Samples and standards will be subjected to the solid phase extraction protocol as included with the kit, using radiolabeled 8-iso-PGF2 $\alpha$ . Particular quality control measures will include the following: When not in use, kit components will be refrigerated. All reagents will be warmed to room temperature before use. Microtiter plates will be allowed to come to room temperature before opening the foil bag. Once the desired number of strips has been removed, the bag will be resealed immediately and stored at 2 – 8°C to maintain plate integrity. Samples will be collected in pyrogen/endotoxin free tubes. Samples will be frozen shortly after collection (1-2 hours) in 500  $\mu$ l aliquots and stored at –20°C to –80°C until further processing, and send on dry ice to the laboratory at CHORI where they will be stored at –80°C, until analysis. Multiple freeze-thaw cycles of frozen samples will be avoided. The sample will be thawed completely and mixed well prior to analysis. When possible, badly hemolyzed or lipemic serum will be avoided. When large amounts of particulate matter are present, samples will be centrifuged or filtered prior to freezing, and a note will be added to indicate this treatment. All Standards, controls and samples will be run in duplicate. Samples that are out of the optimal range (10-500 pg/ml) will be diluted with Standard Diluent Buffer. When pipetting reagents, a consistent order of addition will be maintained from well to well. This ensures equal incubation times for all wells. All reagents will be capped when not in use. Reagents from lots from various kit lots will not be interchanged or mixed. Reagents will not be used after the kit expiration date. Within 2 hours of assay completion, absorbance will be read. In-house controls will be run with every assay. If control values fall outside pre-established ranges, the accuracy of the assay is suspect, and will be repeated. All residual wash liquid will be drained from the wells by efficient aspiration or by decantation followed by tapping the plate forcefully on absorbent paper. Never will absorbent paper be inserted directly into the well. Because stabilized chromogen is light sensitive, prolonged exposure to light will be avoided.

#### 5) EKTAcytometry

Osmotic gradient ektacytometry will be performed using a custom build ektacytometer using a National Instrument interface to a Macintosh computer for instrument control and data analysis using Igor software (Wave metrics, Lake Oswego, Or). The osmotic gradient curve will reflect cellular characteristics based

on surface area to volume ratio, state of hydration and changes in mechanical properties of the membrane. In our experience, RBC samples from normal individuals will render virtually identical results over time. All results will be compared to a standard curve which is a compilation of more than 1000 samples collected over time. Weekly a known sample from a laboratory volunteer will be analyzed and compared to the standard curve as well as their previous results available. A shift of more than 5% in the curve indicates the need for calibration. After calibration, the measurement of is repeated to ensure proper alignment. All samples will be accompanied by travel controls, to ensure proper handling by the carrier. When the travel control falls outside of the normal average range, a laboratory control will be run to ensure proper instrument calibration. All results of patient samples will be stored together with travel controls. Specific quality control measures include: Samples (including travel controls) will be collected in ACD tubes according to protocols provided to the collecting sites, stored at 4°C, and send that same day on wet ice to the laboratory at CHORI by overnight transport. At CHORI the samples will be stored at 4°C, and analyzed as soon as possible. All standards, controls and samples will be run in series.

#### **6) Endothelin-1 (ET-1)**

The ELISA kit to measure ET-1 will be purchased from Cayman chemical (Cayman, Ann Arbor, MI). The kit consists of a 96 well plate, buffers and standard solution. The protocol to measure ET-1 in human serum or plasma will be strictly followed as provided with this commercial kit. All reagents needed for the assay are provided by the company and will be stored and used according to their recommendations, since serum or plasma may contain compounds that interfere with the assay. In particular samples that contain less than 50 pg/ml are prone to render inaccurate results. Hence, the samples will be purified according a standard protocol, using a C-18 reverse phase cartridge (Sep-Pak). Samples and standards will be subjected to the extraction protocol as included with the kit, using standard amounts of ET-1 to spike the samples in the range of 90% with a variance of 20%. Particular quality control measures will include the following: When not in use, kit components will be refrigerated. All reagents will be warmed to room temperature before use. Microtiter plates will be allowed to come to room temperature before opening the foil bag. Once the desired number of strips has been removed, the bag will be resealed immediately and stored at 2 – 8°C to maintain plate integrity. Samples will be collected in pyrogen/endotoxin free tubes. Samples will be frozen shortly after collection (1-2 hours) in 500 µl aliquots and stored at –20°C to –80°C until further processing, and send on dry ice to the laboratory at CHORI where they will be stored at –80°C, until analysis. Multiple freeze-thaw cycles of frozen samples will be avoided. The sample will be thawed completely and mixed well prior to analysis. When possible, badly hemolyzed or lipemic serum will be avoided. When large amounts of particulate matter are present, samples will be centrifuged or filtered prior to freezing, and a note will be added to indicate this treatment. All Standards, controls and samples will be run in duplicate. Samples that are out of the optimal range (10-500 pg/ml) will be diluted with standard diluent buffer. When pipetting reagents, a consistent order of addition will be maintained from well to well. This ensures equal incubation times for all wells. All

reagents will be capped when not in use. Reagents from lots from various kit lots will not be interchanged or mixed. Reagents will not be used after the kit expiration date. Within 2 hours of assay completion, absorbance will be read. In-house controls will be run with every assay. If control values fall outside pre-established ranges, the accuracy of the assay is suspect, and will be repeated. All residual wash liquid will be drained from the wells by efficient aspiration or by decantation followed by tapping the plate forcefully on absorbent paper. Never will absorbent paper be inserted directly into the well. Because stabilized chromogen is light sensitive, prolonged exposure to light will be avoided.

## 10.2 Drug Concentration Measurements

Plasma arginine levels will be measured throughout the study as outlined in the tables above.

## 11 DATA AND SAFETY MONITORING PLAN

### 11.1 Safety Assessments

#### 11.1.1 Safety Monitoring

While no toxicities from oral arginine are expected, we will comprehensively monitor patients to assess for unexpected toxicity. Patients enrolled in this trial will receive all therapy and monitoring that is considered standard of care for patients with SCD. Patients will be asked about signs and symptoms as they relate to their illness and arginine administration. For all patients presenting with chest pain or cardiac events, an EKG will be done and CPK isoenzymes and troponin levels will be measured. To assess potential clinical efficacy, study personnel will collect information on emergency room visits and hospitalizations, clinic visits for pain, and pain medication use. All clinical information will be collected using standardized study forms. As part of this study patients will have regular blood draws to assess safety of arginine. The potential deleterious effects of increased NO production, such as oxidative damage, will be monitored using CBC, chemistry panel, urinalysis, and met Hemoglobin level. Evaluation of these labs will allow for assessment of ongoing effects on organ function and hematopoiesis.

#### 11.1.2 Safety Assessments by Study Visit

The laboratory monitoring by study visit is outlined in the table below:

Test	Week -4	Week -2	Study Entry	Week 1	Week 2	Week 4	Week 8	Week 12	Week 14	Week 16
CBC/retic	X		X	X	X	X	X	X	X	X
Chem panel*	X		X	X	X	X	X	X		X
Urinalysis	X		X	X		X		X		X
Met Hb	X		X	X		X	X	X		
βHCG	X	X	X	X	X	X	X	X	X	
ECHO***			X					X		
EKG, CPK isoenzymes and troponin levels #			X	X	X	X	X	X	X	X

\* Includes Na,K,Cl,CO2,Ca,BUN,Cr,gluc,total protein,alb,total bili,ALT,alk phos,LDH

\*\*\*The second echocardiogram will be performed at week 12 only if the first echocardiogram is abnormal at Study Entry.

#These additional tests need to be done for all prospective chest pain events for patients in this study.

## 11.2 Adverse Events

### 11.2.1 Definitions of Adverse Events and Serious Adverse Events

An adverse event (AE) is defined for this study as any untoward medical occurrence in a patient or clinical investigation subject administered a pharmaceutical product that does not necessarily have a causal relationship with this treatment. An AE can therefore be any unfavorable and unintended sign (including an abnormal laboratory finding), symptom, or disease temporally associated with the use of a medicinal (investigational) product, whether or not related to the medicinal (investigational) product. AE data are recorded on the CRF form.

A serious adverse event (SAE) is defined as any untoward medical occurrence that at any dose:

- Results in death;
- Is life-threatening (i.e. an event in which the subject was at risk of death at the time of the event; it does not refer to an event which hypothetically might have caused death if it were more severe).
- Requires inpatient hospitalization or prolongation of existing hospitalization.
- Results in persistent or significant disability/incapacity.
- Results in a congenital anomaly/birth defect.
- In the opinion of the investigator, important medical events that may not be immediately life-threatening or result in death or hospitalization but may jeopardize the subject or may require intervention to prevent one of the other outcomes listed in the definition above, may be considered serious. Examples of such events are intensive treatment in an emergency room or at home for allergic bronchospasm; blood dyscrasias or convulsions that do not result in hospitalization; or development of drug dependency or drug abuse.

An *expected SAE* for subjects in this study is an adverse event that is listed in Table 11.1 and is a serious adverse event, as defined above. An *unexpected SAE* for subjects in this study is any AE that is **not** listed in Table 11.1 and is a serious adverse event, as defined above.

Table 11.1. List of Expected Adverse Events in This Study

Expected AE	Expected AE	Expected AE
Acute chest syndrome	Pyelonephritis	Hypoxemia (PO 2 < 65mm Hg)
Anemia	Renal failure	Infection, pneumococcal
Aplastic crisis	Renal insufficiency/albuminuria	Jaundice
Aplastic crisis/anemia	Renal papillary necrosis	Leukocytosis
Arthralgia	Reticulocytosis (≥10%–20%)	Meningitis
Avascular necrosis of hip/shoulder	Retinal disease	Rhabdomyolysis
Avascular necrosis of the femoral head	Retinal hemorrhage	Sepsis
Bone infarction	Elevated urinary urobilinogen	Skin ulcers
Cardiomegaly	Fever	Splenic sequestration
Cerebrovascular accident	Hand-foot syndrome	Pain, joint
Cholecystitis, hepatic sequestration	Hematuria	Pain, long bone
Cranial nerve palsy	Hemiplegia	Pain, severe abdominal
Decreased kidney function	Hemolysis	Priapism
Decreased lung function	Hepatosplenomegaly	Pulmonary embolism
Delayed growth/puberty	Hyperplastic bone marrow	Pulmonary hypertension
Depressed ESR	Hyposthenuria	Pulmonary parenchymal infiltrates on chest x-ray

Table 11.2. Overview of Definitions of Safety Measures

Word or Phrase and (Abbreviation)	Definition
Adverse event (AE)	Any untoward clinical or medical occurrence.
Serious adverse event (SAE)	Any adverse event that results in any of the following outcomes: Death, a life-threatening adverse event, inpatient hospitalization or prolongation of existing hospitalization, a persistent or significant disability/incapacity, or a congenital anomaly/birth defect.
Expected Serious Adverse Event (Expected SAE)	An expected SAE for subjects in this study is an adverse event that is listed in Table 11.1 and is a serious adverse event, as defined above.
Unexpected Serious Adverse Event (Unexpected SAE)	An unexpected SAE for subjects in this study is any AE that is not listed in Table 11.1 and is a serious adverse event, as defined above.
Adverse Clinical	Any safety laboratory measurement that is measured beyond the

Laboratory Results	acceptable limits (either high or low) for the population being studied, as described by the investigator.
--------------------	--

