### 11.2.8 Reporting of Safety Laboratory Measures

Six months after the first subject is enrolled in the study, and at the end of each 6 months thereafter, the SDMC will:

- Make a “snapshot” copy of the study’s clinical laboratory data.
- Perform an appropriate statistical analysis of clinical laboratory change-from-baseline data for each clinical laboratory evaluation obtained in this study.
- Perform an appropriate statistical test of:  $H_0$ : The mean (or median, or proportion, as appropriate) change-from-baseline of the clinical laboratory values for the active treatment group is the same as for the placebo group, vs.  $H_a$ : The mean (or median, or proportion) change-from-baseline in the active treatment group is “worse” than for the placebo group. The meaning of “worse” depends upon the specific clinical lab measurement. The test statistic p-value is not adjusted for multiplicity.
- If the hypothesis test p-value is less than the critical value shown in Table 3, the SDMC will conduct further statistical analyses as indicated by the circumstances and highlight this finding in the semi-annual DSMB report.
- Collaborate with the Principal Investigator to incorporate the results into the study’s semi-annual report to the DSMB and the NHLBI Project Officer.

Table 11.3. Summary of Procedures and Timing for Alerting the DSMB and NHLBI Project Officer of Possible Serious Safety Issues

Situation or Event	Summary of Procedure (See text for details.)	Critical Value for DSMB “Alert”
Unexpected SAE	1. Site investigator notifies SDMC SAE Regulatory Specialist and Principal Investigator within 8 hours.	Alert all cases.
	2. Site investigator, SDMC SAE Regulatory Specialist and Principal Investigator prepare report using FDA forms and submit report to DSMB, NHLBI Project Officer, IRBs, study investigators. Report: 1. Fatal or life-threatening: within 7 calendar days. 2. Otherwise: within 14 calendar days.	Alert all cases.
Expected SAE	SDMC performs quarterly analyses of MedDRA-coded SAEs, tabulates patients with SAEs classified by highest level MedDRA term. Report only when $p <$ critical value and active treatment group has higher AE rate.	$p < 0.01$ $p$ not adjusted for multiplicity

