Adverse Events (all)	SDMC performs semi-annual analyses of MedDRA-coded AEs, tabulates patients with AEs classified by highest level MedDRA term. Report every 6 months. Alert only when FET $p <$ critical value and active treatment group has higher AE rate.	$p < 0.01$ $p$ not adjusted for multiplicity
Adverse	SDMC performs semi-annual analyses of clinical lab	$p < 0.005$

Clinical Lab Results	change-from baseline using analyses appropriate for the data type. Report every 6 months. Alert only when $p < \text{critical value}$ and change is in “adverse” direction.	p not adjusted for multiplicity
----------------------	---	---------------------------------

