#### *12.4.3 Safety Data*

The assessment of safety data will be based mainly on the tabulation of adverse events (AE), by age group and treatment arm. Additionally, AEs will be tabulated by severity and relationship to drug. Serious AEs will be described in detail. Additionally, blood chemistry, hematology, and urinalysis laboratory measurements will be tabulated by age group, treatment group, and measurement time. Other specific laboratory measurements, such as Met Hb, will also be collected and tabulated by age group, treatment group, and measurement time.

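### The laboratory safety alert tests only an arm-level change from baseline, not the out-of-limit patient values that the protocol defines as adverse laboratory results

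*Protocol*

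**What the plan says.** **Definition.** Protocol Table 11.2 (section 11.2.1) defines adverse clinical laboratory results at the level of the single value: "Any safety laboratory measurement that is measured beyond the" "acceptable limits (either high or low) for the population being studied, as described by the investigator".

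**Alert.** For the semi-annual look, section 11.2.8 tells the data center to "Perform an appropriate statistical analysis of clinical laboratory change-from-baseline data for each clinical laboratory evaluation obtained in this study". The null hypothesis is: "The mean (or median, or proportion, as appropriate) change-from-baseline of the clinical laboratory values for the active treatment group is the same" as for placebo. The alternative is that the active arm is worse, so the test is one-sided. "The test statistic p-value is not adjusted for multiplicity". The row of Table 11.3 named after the definition repeats this ("change-from baseline using analyses appropriate for the data type") and sets the critical value at p < 0.005 with the change in the adverse direction.

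**Final analysis.** Section 12.4.3 says that "blood chemistry, hematology, and urinalysis laboratory measurements will be tabulated by age group, treatment group, and measurement time".

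**Related rules.** Sections 8.3, 9.1.2 and 11.2.9 list patient-level laboratory criteria for stopping arginine: hemoglobin, SGPT with albumin, creatinine and methemoglobin. Section 5.6 notes hyperkalemia in advanced renal or hepatic insufficiency.

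**The concern.** One term carries two meanings inside section 11.2. The definition concerns a patient whose value is out of limits. The alert concerns the location of a whole arm's distribution. The laboratory harms that the protocol names are threshold crossings in individuals, and a handful of these moves an arm mean or median very little.

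The primary objective (section 6) covers deleterious as well as beneficial effects. If a few arginine patients had marked laboratory changes and placebo patients had none, the rule written to highlight adverse laboratory results would usually stay silent. No stated step would set the number of affected patients side by side by arm.

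**Working it through.** The protocol states a critical value but no operating characteristic for the alert, so there is no figure of its own to reproduce. The check is how often the stated rule fires.

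**Inputs from the protocol**
- One-sided p < 0.005 (section 11.2.8, Table 11.3).
- 16 low-dose and 16 placebo patients per age group (section 7.2). This is the arm size if section 12.3.4, which stratifies all analyses by age, also governs the alert. Pooling the ages gives 32 vs 32.
- Adding the 16 + 14 = 30 earlier high-dose patients to the active side gives 62 vs 32.

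**Assumptions (the protocol gives no laboratory SD)**
- Changes are normal with SD 1.
- k arginine patients are shifted by d = 3, 5 or 8 SD; no placebo patient is.

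**Mean or rank test, single look (simulation).** Range over d and over the pooled t, Welch and rank tests:

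| Affected on arginine | 16 vs 16 | 32 vs 32 |
|---|---|---|
| 2 | 0.1-1.6% | 0.6-1.6% |
| 3 | 0.4-3.3% | 1.6-3.1% |
| 4 | 2.4-7.4% | 2.4-5.9% |

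The Welch test stays at about 6% or below throughout. The 7.4% is the pooled-variance t test with 4 of 16 shifted by 5 SD. With 62 vs 32 and 1 to 4 affected, the range is 0.3-5.5%. With nobody affected the rate is about 0.2-0.5%.

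**Why a bigger shift need not help.** With n per arm, the mean difference is kd/n, and the active-arm variance is about 1 + d²·k(n−k)/[n(n−1)]. Take n = 16, k = 2, d = 8:
- Mean difference: 2 × 8/16 = 1.0.
- Variance: 1 + 64 × 28/240 = 8.47.
- Standard error: √[(8.47 + 1)/16] = 0.77.
- t is centred near 1.0/0.77 = 1.3, against a one-sided 0.005 critical value of 2.75 on 30 df.

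In simulation the pooled t test falls from about 1.5% at 3 SD to 0.2% at 8 SD in this case.

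**Repeated looks.** With three cumulative looks at an assumed 11, 22 and 32 per arm (pooled t test), the chance of at least one alert is 2.3% for 2 affected, 2.4-4.0% for 3 and 7.8% for 4.

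**Proportion option.** Against zero on placebo with equal arms, the one-sided Fisher p is C(n,k)/C(2n,k).
- n = 16: k = 6 gives 8,008/906,192 = 0.0088; k = 7 gives 11,440/3,365,856 = 0.0034. Seven are needed.
- n = 32: k = 7 gives 0.0054; k = 8 gives 0.0024. Eight are needed.
- 62 vs 32: twelve are needed.
- For scale, 4/32 vs 0/32 gives 35,960/635,376 = 0.057 one-sided (0.11 two-sided).

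**The adverse-event route.** Section 11.2.1 lets an abnormal laboratory finding be an AE. It then enters a yes/no table per highest-level MedDRA term, with a Fisher alert at p < 0.01. Two-sided, and before dilution by other events under the same term, that also needs 7/16 or 8/32 against none.

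**The case against.** The strongest reply is that the alert does not control what the DSMB sees. Laboratory results go into every semi-annual report whatever the p-value; crossing 0.005 only adds further analyses and a highlight. Section 13.1 has the DSMB examine unblinded safety data periodically. Every unexpected SAE is reported case by case. Hyperkalemia and methemoglobinemia are not in Table 11.1, so serious instances would take that route. Patients who meet the laboratory stopping criteria are taken off arginine individually. All of this stands.

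A reader might therefore infer too much: that severe laboratory toxicity would be hidden from the DSMB, or averaged away in the final tables. The documents do not support either. The reporting routes above rule out the first. On the second, section 12.4.3 says that measurements are tabulated, prescribes no averaging, rests the safety assessment mainly on AE tabulations and has serious AEs described in detail.

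It can also be said that section 11.2.8 permits a proportion, which could count out-of-limit patients. It could, but the text does not tie the proportion to the Table 11.2 definition, and at these arm sizes the p-value gate leaves it insensitive too.

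Finally, out-of-range counts and listings often belong in an SAP or a DSMB report template, and their absence alone would be no finding. Here, however, the protocol itself fixes an alert rule under a defined name and does not use the definition.

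**Conclusion.** The point holds in limited form. The laboratory alert does not analyse the quantity that Table 11.2 defines. For 2 to 4 affected patients in the arginine arm it fires in roughly 0.1-6% of trials on a mean-based Welch test (up to 7.4% with the pooled t test). It becomes likely only when many are affected: with 8 of 16, 54-99.5% by t or Welch but still only 36-40% by the rank test. The rates rest on an assumed normal scale and assumed shifts; the conclusion is the same across 3 to 8 SD and all arm sizes tried.

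What falls through is limited to two kinds of case. The first is the non-serious out-of-limit value. The second is the laboratory-type event on the expected list, such as anemia, renal failure, decreased kidney function or hemolysis. Even when serious, these raise an alert only through the p < 0.01 comparison by highest-level MedDRA term. For neither does a stated step count, by arm, the patients who crossed a laboratory limit. This is worth correcting because the correction is cheap; it is not a failure of safety oversight as a whole.

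**What to change.** Link the Table 11.2 definition to section 11.2.8 and Table 11.3, and carry it into section 12.4.3:

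- In every semi-annual DSMB report, whatever the p-value, give per laboratory test, arm and age group the number of patients whose post-dose value newly crosses a prespecified limit (pre-dose values did not) or meets a laboratory discontinuation criterion. Add a listing of those patients.
- Replace limits left to the investigator's description with limits fixed in advance. The sponsor sets them and reconciles them with sections 8.2 and 8.3. Those sections cannot simply be copied: the entry and discontinuation values differ, SGPT and methemoglobin are multiples of normal, and neither section has a potassium limit.
- Keep the change-from-baseline test as a supplement. Do not put the new count behind another p-value gate, since 4/32 vs 0/32 would not pass one.

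The cost is protocol wording plus one table and one listing from data already collected. The downside is a slightly longer DSMB report in which some listed values will prove to be noise.
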